Phase	Phase I (proof of concept, prospective, interventional, open label single group assignment)
Methodology	Open label with matched de-identified retrospective control cohort
Study Duration	Approximately 24 months
Study Center(s)	Single Center in the United States – University of Michigan, Ann Arbor
Objectives	
Primary Objective:
 
Safety of uproleselan in patients with severe COVID-19 pneumonia.
 
Secondary Objectives:
 
To evaluate if treatment with uproleselan administered intravenously in addition to the best available therapy according to institutional guidelines is able to reduce the progression of acute respiratory failure, in patients with severe COVID-19 pneumonia.
 
 ● To evaluate overall survival and all-cause mortality at day 15 and 28. ● To evaluate changes in the COVID ordinal outcomes scale. ● To assess adverse events to evaluate the safety of uproleselan. ● To assess ventilator-free days, ICU-free days, oxygen, vasopressor free days. ● To evaluate changes in D-dimer. 
Exploratory Objectives:
 
 ● To examine the correlation of plasma soluble E-selectin concentrations with clinical outcomes. ● To examine the correlations of other biomarkers of interest with clinical outcome.
Number of Subjects	15 subjects will be enrolled in the experimental cohort to receive uproleselan. with 1:1 matched de-identified retrospective control cohort. (n=15)
Inclusion Criteria	
 1. Adults, ages 18 – 85 years. 2. Willing and able to provide informed consent prior to performing study procedures unless they have a legally authorized representative (LAR). 3. Documented COVID-19 pneumonia: defined as upper respiratory tract specimen (nasopharyngeal swab (NPS) or viral throat swab) positive for COVID-19 and imaging (CXR/CT scan) suggestive of COVID-19 pneumonia. 4. Confirmed coronavirus (SARS-CoV-2) infection, enrolled ≤ 48 hours of beginning oxygen need for COVID-19+ confirmed hospital admission.

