5.1.1 Treatment Plan

Up to 15 subjects will be enrolled in this prospective, interventional, single-arm, open label trial. All drug administration will be performed by nurses in the inpatient unit. Uproleselan injection is a sterile solution for IV administration, supplied in single-dose vials at a concentration of 50 mg/mL. Uproleselan should be administered intravenously (IV) into a peripheral line, a central catheter, or a peripherally inserted central line catheter (PICC). Infusion should take place at a steady rate over a period of 20 minutes \pm 2 minutes using a syringe pump or IV pump. Microbore tubing is preferred. In-line filtration is highly recommended. Dilution of uproleselan may be performed with normal saline (0.9% Sodium Chloride) up to 5x as needed for ease of administration and per institutional practice. Compatibility with other therapeutic agents has not been determined, therefore uproleselan should not be administered concurrently with anything other than saline. When flush is used, saline flush is preferred.

Table 2: Description of Treatment

Agent	Premedications/ Precautions	Dose	Route	Schedule
Uproleselan (GMI-1271)	None	20 mg/kg BID, up to a maximum dose of 2500 mg	IV infusion over 20 min	Daily on treatment days 1-7

Table 3: Standard of Care Treatments

1. Supplemental oxygen, escalate to heated high flow nasal cannula, noninvasive ventilation, endotracheal intubation and mechanical ventilation as needed.
2. Conservative fluid management strategy.
3. Dexamethasone 6mg (PO or IV) qD for up to 10d (RECOVERY trial, Horby PW et al.³⁸
4. Remdesivir 200 mg loading dose, then 100 mg daily for up to 9 additional days (ACTT-1 Study, Beigel JH et al.).³⁹
5. Convalescent plasma for compassionate use.
6. Other medical management as recommended by Infectious Disease Consultants.
7. Management of septic shock.
8. ICU admission as required.

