5.2 Assessment for Toxicities

Any subject who receives treatment on this protocol will be evaluable for toxicity. Each subject will be assessed for the development of toxicity according to the Time and Events Table (Table 3). Toxicity will be assessed according to the CTCAE v. 5.

All drug administration will be performed by nurses in the inpatient unit. Routine vital sign measurement will be performed and all adverse events (AEs) will be recorded. Toxicities will be classified as AEs probable, possible, unlikely or unrelated to uproleselan.

5.2.1

Evaluating for progression to Acute Respiratory Failure

- Reduction in the progression to acute respiratory failure [Time Frame: 15 days].
- Patients with a baseline PaO₂/FiO₂ \geq 200: progression of respiratory failure is defined by:
 - a. severe gas transfer deficit (PaO₂/FiO₂ < 200).
 - b. persistent respiratory distress while receiving oxygen (persistent marked dyspnea, use of accessory respiratory muscles, paradoxical respiratory movements).
- The rate will be calculated as the proportion of patients who experienced at least one of the events above by day+15 from treatment start.
- Overall survival and all-cause mortality (day 15, day 28).
- Time to improvement in oxygenation for at least 48 hours. Improvement in oxygenation is defined as an increase in PaO₂/FiO₂ of 50 (or greater) compared to the nadir of PaO₂/FiO₂.
- Number of patients requiring mechanical ventilation, if not on mechanical ventilation at study entry.
- Change in the WHO COVID-19, “8-point ordinal scale” from study entry to day 28 (Table 1). To be assessed on day 3, day 8, day 15, day 28.
- Duration of hospitalization and duration of ICU care.
- Toxicity assessment (including incidence of grade 3-5 hemorrhagic events).
- Change in D-dimer [Time Frame: baseline, study day 3, day 8, day 15, and day 28]. Changes in plasma D-dimer level compared with baseline at enrollment.
- Decrease or Change in IL-6:IL-10 ratios.

- Free-Days- at day 28
Oxygen
Ventilator
Vasopressor
ICU
Hospitalization

Table 1: WHO Ordinal Scale Ordinal Score

Patient State	Descriptor	Score
Ambulatory	No limitation of activities	1
	Limitations of activities	2
Hospitalized (mild disease)	No oxygen therapy	3
	Oxygen by mask or nasal prongs	4
Hospitalized (severe disease)	Non-invasive ventilation or high-flow oxygen	5
	Intubation and mechanical ventilation	6
	Mechanical ventilation + additional organ support – pressors, RRT, ECMO	7
Dead	Death	8

Exploratory Endpoints

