5.7 Subject Replacement

Subjects will be replaced in this study if they are removed.

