12 STATISTICAL CONSIDERATIONS

12.1 Study Design/Study Endpoints

This is a prospective, interventional, single-arm, open label trial, with 1:1 matched de-identified retrospective control cohort. Study subjects will receive uproleselan IV BID x 7 days. 15 patients who consent to drug administration will be enrolled in the treatment arm.

Primary Endpoints: Safety

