12.1.2. Additional Interim Safety Assessment (Study Sample Size: 15 patients)

An interim assessment for toxicity and early mortality will be performed after the first 5 patients have enrolled, and again after the first 10 patients are enrolled. Accrual may proceed to a maximum of 15 patients, if the stopping rules are not met within the first 5 patients.

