12.3 Data Analyses Plans

Descriptive statistics will be calculated for quantitative safety data, as well as change from baseline. Frequency counts will be compiled for classification of qualitative safety data.

Secondary endpoints include reduction in the progression to acute respiratory failure. For patients with a baseline PaO₂/FiO₂ \geq 200: progression of respiratory failure is defined by:

- severe gas transfer deficit (PaO₂/FiO₂ < 200);
- persistent respiratory distress while receiving oxygen (persistent marked dyspnea, use of accessory respiratory muscles, paradoxical respiratory movements);

The rate will be calculated as the proportion of patients who experienced at least one of the events above by day+15 from treatment start.

There are many other secondary endpoints, but two of the most important are: (i) Day 28 overall survival and (ii) Day 28 ventilator free survival, both of which are binary endpoints. Day 28 overall survival will be summarized by the proportion of the twelve patients who are alive at Day 28 after starting treatment, and Day 28 ventilator-free survival will be summarized by the proportion of the twelve patients who are both alive and not using a ventilator at Day 28 after starting treatment. Both proportions will be

accompanied by an exact 95% confidence interval. All other secondary endpoints will be collected and assessed.

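### Section 12.3 takes both key Day 28 proportions over twelve patients, but the treated cohort is 15 and no set of twelve is defined

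*Combined protocol and SAP*

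**What the plan says.** Section 12.3 singles out two binary secondary endpoints and says how each is summarized. For overall survival: "Day 28 overall survival will be summarized by the proportion of the twelve patients who are alive at Day 28 after starting treatment". For ventilator-free survival: "the proportion of the twelve patients who are both alive and not using a ventilator at Day 28 after starting treatment". Both proportions are to carry an exact 95% confidence interval.

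The size of the treated cohort is stated in several other places:

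- Study Synopsis, Number of Subjects: "15 subjects will be enrolled in the experimental cohort to receive uproleselan". The synopsis entry on statistical methodology also gives 15.
- Section 12.1, with the same sentence in Section 12.2: "15 patients who consent to drug administration will be enrolled in the treatment arm".
- Section 5.1.1: "Up to 15 subjects will be enrolled in this prospective, interventional, single-arm, open label trial".
- Section 12.1.2, repeated in Section 13: "Accrual may proceed to a maximum of 15 patients".

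**The concern.** For a binomial proportion with an exact interval, the denominator is one of only two inputs. Here it disagrees with every statement of the cohort size, and the patients it refers to cannot be identified. The number is spelled out as a word, twice, in intact sentences, so it is not a reading error from the PDF.

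The consequence is that the plan does not say who is counted. Whoever runs the analysis must decide, and in an open-label single-arm trial that decision would be made with the outcomes known. Section 12.2 says the results are meant to inform the design of later studies, so the survival figures are likely to be carried forward.

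**Working it through.** **Inputs.** Stated denominator: 12, for both endpoints (Section 12.3). Treated cohort: 15 (Study Synopsis, Sections 12.1 and 12.2) or at most 15 (Sections 5.1.1, 12.1.2 and 13). Interval: exact, 95% (Section 12.3), taken here to mean Clopper-Pearson, two-sided. Section 12.2 states that the sample size does not rest on a power calculation, so there is no derived figure to reproduce. Survivor counts below are assumed.

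**Step 1: is twelve defined anywhere?**

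- Sections 12.1.2 and 13 place interim assessments after 5 and 10 patients.
- Section 13 counts bleeding in the first 10, and deaths in the first 6 and first 11.
- No evaluable, per-protocol or other analysis set of twelve appears.
- The only other groups of 12 are the survivors and the deaths in the biomarker series in Section 1.2, who are not trial patients.

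**Step 2: size of the mismatch.** 15 − 12 = 3 patients, and 3/15 = 20% of the planned cohort. Because the cohort is also written as a maximum, fewer than 15 may be treated, but that does not fix the number at twelve. If fewer than twelve were treated, the rule could not be applied at all.

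**Step 3: effect on the interval.** For x survivors of n, the lower limit is the 2.5th percentile of Beta(x, n − x + 1) and the upper limit is the 97.5th percentile of Beta(x + 1, n − x).

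Same observed proportion, two-thirds:

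- 8/12: Beta(8, 5) gives 34.9% and Beta(9, 4) gives 90.1%. Width 90.1 − 34.9 = 55.2 points.
- 10/15: Beta(10, 6) gives 38.4% and Beta(11, 5) gives 88.2%. Width 88.2 − 38.4 = 49.8 points.
- Difference in width: 55.2 − 49.8 = 5.4 points.

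Other points on the range:

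- Widest interval with n=12: 6/12, from 21.1% to 78.9%, width 57.8 points.
- Widest interval with n=15: 8/15, from 26.6% to 78.7%, width 52.1 points (7/15 has the same width).
- No deaths: the lower limit is 73.5% for 12/12 and 78.2% for 15/15.

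**The case against.** The strongest reply is that this is a stray number with little practical effect. The sentence speaks of patients who started treatment and every other statement gives 15, so a sensible analyst would probably count all treated patients. The result would then be the one intended. No test or decision rule uses these endpoints, the pilot is not powered, and the primary endpoint is safety. All of that stands and limits the weight of the point. It does not remove the mismatch: this is the only computing rule given for two endpoints that the plan itself ranks highly, and the sensible choice would be made outside the plan.

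Three stronger readings are tempting, and the documents support none of them.

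- A reader might infer that survivors among all 15 would be divided by 12, inflating survival. The wording takes numerator and denominator from the same twelve, so it does not imply that error or any predictable direction of bias.
- A reader might try to explain the twelve, for instance by 20% loss (12/0.80 = 15) or by the mortality rule in Section 13. No dropout rate is stated. That rule looks at the first 6 and first 11 patients, which neither supplies a set of twelve nor shows where the number came from.
- A reader might infer that replacement hides deaths, because Section 5.7 says "Subjects will be replaced in this study if they are removed" without saying whether dosed patients who are replaced stay in these proportions. That detail is missing, but no removal rate is given, so no size can be attached to it. The documents also point towards capture. Section 5.6 asks subjects taken off study to follow safety procedures where possible, Section 5.2 says "Any subject who receives treatment on this protocol will be evaluable for toxicity", and Section 8.2.1 collects serious adverse events for 28 days from the first dose. These provisions do not set the Day 28 analysis set, but they give no ground for alleging concealed deaths.

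**Conclusion.** The denominator in Section 12.3 is wrong as written, for both Day 28 endpoints. This is an internal inconsistency rather than a failed calculation. Taken literally, the rule leaves out up to three treated patients without saying which, and costs about 5 points of interval width at an observed two-thirds. If the analyst uses all treated patients instead, the numerical effect is nil and only the pre-specification is lacking.

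The mismatch itself rests on no assumption. The interval figures assume Clopper-Pearson limits, illustrative survivor counts and a full cohort of 15. The text should be corrected because the endpoints are prominent and the correction is easy. The primary safety endpoint is not affected.

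**What to change.** In both places in Section 12.3, replace the reference to twelve patients with: *all patients who received at least one dose of uproleselan (planned n=15), including any later removed or replaced*. Report the number with unknown Day 28 status beside each proportion. The denominator is then the number actually dosed, which may differ from 15 if accrual stops early or dosed patients are replaced.

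The cost is one phrase changed twice in a single amendment. Note f to the schedule in Section 6.2 already plans a remote contact at Day 28, so no visit is added. Removed patients who have not withdrawn consent to follow-up would also need that contact. Counting them could move the estimates slightly in either direction.

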COVID-19 ARDS appears to have worse outcomes than ARDS from other causes. The intensive care unit and hospital mortality from typical ARDS are 35.3% (95% CI, 33.3–37.2%) and 40.0% (95% CI, 38.1–42.1%), respectively.⁶ For COVID-19 ARDS, mortality ranged between 26% and 61.5% if ever admitted into a critical care setting, and in patients who received mechanical ventilation, the mortality can range between 65.7% to 94%. Risk factors for poor outcomes include older age; presence of comorbidities such as hypertension, cardiovascular disease and diabetes mellitus; lower lymphocyte counts; kidney injury; and raised D-dimer levels. Death from COVID-19 ARDS is due to respiratory failure (53%), respiratory failure combined with cardiac failure (33%), myocardial damage and circulatory failure (7%), or death from an unknown cause.⁷

Given the high mortality rate associated with COVID-19 ARDS, preventing progression of COVID-19 pneumonia in patients simply requiring supplemental oxygen to COVID-19 ARDS is a key priority and goal.

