4.2 Exclusion Criteria

1. In the opinion of at least one investigator, unlikely to survive for >48 hours from screening.
2. Severe chronic respiratory disease (e.g. COPD or other) requiring supplemental oxygen and/or having required mechanical ventilation pre-COVID-19 infection.
3. Concurrent enrollment in a COVID related interventional drug trial. Use of remdesivir, steroids, and convalescent plasma are permitted along with other standard of care therapies for COVID.³⁷
4. Currently on invasive mechanical ventilation.
5. Hypotension defined as systolic blood pressure < 90 mmHg on two sequential readings at least 4 hours apart.
6. Total Bilirubin ≥ 3 x upper limit of normal (ULN), Creatinine Clearance ≤ 30 mL/min/1.73m².
7. Pregnant or breastfeeding.
8. Known diagnosis of an acute thrombosis on admission.
9. Concurrent dual antithrombotic therapy (aspirin or P2Y₁₂ inhibitor plus anticoagulation to treat deep venous thrombosis or pulmonary embolism (single antiplatelet or anticoagulant agent at prophylactic dose is permitted).
10. Concomitant use of thrombolytic therapy.
11. Concomitant therapeutic systemic anticoagulant therapy (e.g. heparin, warfarin, direct thrombin inhibitors and direct factor Xa inhibitors). As per NIH Guidelines: Hospitalized adults with COVID-19 should receive VTE prophylaxis per the standard of care for other hospitalized adults (AIII). Anticoagulant or antiplatelet therapy should not be used to prevent arterial thrombosis outside of the usual standard of care for patients without COVID-19 (AIII); <https://www.covid19treatmentguidelines.nih.gov/therapeutic-management/>
12. History of recent major bleeding, defined in accordance with the criteria of the International Society on Thrombosis and Hemostasis (ISTH).
13. History of bleeding disorder thought to impose excessive bleeding risk as per investigator discretion
14. Hemodynamic instability, defined as inability to maintain mean arterial pressure.
15. Hypersensitivity to the active substance or to any of the excipients of uproleselan.
16. Any physical examination findings and/or history of any illness that, in the opinion of the investigator, might confound the results of the study or pose an additional risk to the patient by their participation in the study

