6.1.1 Procedures during Study Drug Treatment Visits

If a laboratory parameter has been obtained within 48 hours prior to study enrollment, it does not need to be repeated for study purposes and will be considered the *baseline* value. Following the last day of study, no further “study related” blood tests will be obtained.

Guidelines for monitoring hematologic and coagulation parameters were derived from Thachil, J., et al., *ISTH interim guidance on recognition and management of coagulopathy in COVID-19*. *J Thromb Haemost*, 2020. **18**(5): p. 1023-1026.⁴²

- **Pulmonary Indices:** Pulmonary parameters will be recorded daily for subjects from the time of study entry to cessation of study drug therapy. Pulmonary assessment will include a subject’s current level of supplemental oxygen support (%FiO₂), current modality of support (mechanical ventilation, BiPaP, CPAP, nasal cannula, or none), and the results of any chest radiographs (if performed) that day. For patients that remain hospitalized on day 15 or 28 of study, pulmonary indices will also be made at that time point. Blood gas values will be obtained as clinically indicated. Scoring from the WHO COVID Ordinal Scale (Table 1) will be determined as indicated by study investigators or study coordinators.
- **Hematologic parameters:**
A complete blood count including platelets (CBCP) should be obtained at baseline (study entry), and daily until cessation of study therapy. Additional blood counts may be obtained as clinically indicated.
- **Chemistries:**
Serum chemistries (Electrolytes, BUN, creatinine, liver panel) should be obtained at baseline (study entry), and daily until cessation of study therapy. Additional chemistries should be obtained as clinically indicated.
- **Coagulation Labs:**
D-dimer, Prothrombin time (PT), activated partial thromboplastin time (aPTT), and serum fibrinogen should be obtained at baseline (study entry). Additional D-dimer, PT, and serum fibrinogen testing may be obtained as clinically indicated.
- **Serologic Cytokine Profiles:** Biomarkers will be drawn on day 0-1 pre-study drug administration, days 1-7, day 15, and day 28. These will be used to measure e-selectin levels and are not for safety labs. Due to current hospital understaffing, blood draws will occur as staffing permits. Missed blood draws will not be counted as protocol deviations.

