12.2 Sample Size and Accrual

This is a pilot proof of concept feasibility study. 15 patients who consent to drug administration will be enrolled in the treatment arm.

The sample size determination was not based on statistical power analysis but is large enough to provide adequate information regarding safety, and to contribute to the design of subsequent studies, and is the number of patients that we can expect to accrue in the current setting of the SARS-CoV2 pandemic.

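### Day 28 ventilator-free survival is scored by ventilator status on Day 28 alone, so a survivor intubated and extubated before then counts as ventilator-free

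*Combined protocol and SAP*

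**What the plan says.** Section 12.3 says of the secondary endpoints that "two of the most important are: (i) Day 28 overall survival and (ii) Day 28 ventilator free survival, both of which are binary endpoints". Success on the second of these means being "both alive and not using a ventilator at Day 28 after starting treatment". The section also fixes the denominator: "Day 28 ventilator-free survival will be summarized by the proportion of the twelve patients". Each of the two rates is to be "accompanied by an exact 95% confidence interval". This is the only definition of ventilator-free survival in the plan. The endpoint lists in Sections 3.2, 5.2.1 and 12.1.3 do not contain it. They do contain a count of patients who come to need mechanical ventilation, and ventilator free-days at Day 28.

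The surrounding text sets the context:

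- Section 4.2, exclusion 4, rules out patients "Currently on invasive mechanical ventilation".
- Section 2.2 sets reduced progression of acute respiratory failure as the leading secondary objective, and Section 1.1 says that "preventing progression of COVID-19 pneumonia in patients simply requiring supplemental oxygen to COVID-19 ARDS is a key priority and goal".
- Section 6.1.1 records "current modality of support (mechanical ventilation, BiPaP, CPAP, nasal cannula, or none" as part of the pulmonary indices. Table 1 scores non-invasive ventilation as 5 and intubation with mechanical ventilation as 6 or 7.
- Section 12.2 states that "15 patients who consent to drug administration will be enrolled in the treatment arm", which does not agree with the twelve in Section 12.3.

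**The concern.** Everyone enters off invasive ventilation, so any intubation on study is a new event and bears directly on the question of progression. An endpoint called ventilator-free survival is naturally read as survival without that event. The scoring sentence measures something else, namely where the patient stands on one day. A patient ventilated from Day 3 to Day 27 and a patient never intubated receive the same score.

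The same section scores its progression endpoint cumulatively, as at least one qualifying event by Day 15, so the status-only rule departs from the plan's own approach to progression. The word *ventilator* is also left open. If it took in BiPAP or CPAP, a patient on CPAP on Day 28 would fail while one extubated the day before would succeed.

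What is at stake is interpretation. Section 12.2 says that the trial should inform the design of later studies. A rate carried forward under this label could be taken for the proportion who survived without intubation when it is not.

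**Working it through.** The plan gives no expected rate, threshold or power for this endpoint, so there is no figure to reproduce. The check compares the two scoring rules.

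**Notation.** Let n be the patients analysed, d the deaths by Day 28, k the survivors still on invasive ventilation on Day 28, and e the survivors intubated after treatment start and off the ventilator by Day 28. Take *ventilator* to mean invasive ventilation throughout.

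- Overall survival = (n − d)/n
- Snapshot, as in Section 12.3 = (n − d − k)/n
- Alive and never intubated = (n − d − k − e)/n

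**Differences.**

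- Snapshot minus never-intubated = e/n. This is never negative, so the snapshot equals or exceeds the never-intubated rate.
- Overall survival minus snapshot = k/n.

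**Size per patient.** 1/15 = 6.7 percentage points with the 15 of Section 12.2. 1/12 = 8.3 points with the twelve of Section 12.3.

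**Plausible number of such patients.** The plan gives no intubation rate, so 4 intubations is an assumption. Section 1.1 cites mortality of 65.7% to 94% in mechanically ventilated patients with COVID-19 ARDS. Taking this as mortality by Day 28 (the section states no time horizon):

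- Expected survivors at 65.7% mortality: 4 × 0.343 = 1.37, and 1.37/15 = 9.1 points.
- Expected survivors at 94% mortality: 4 × 0.06 = 0.24, and 0.24/15 = 1.6 points.

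These are ceilings, because they treat every intubated survivor as off the ventilator by Day 28. Any who are still ventilated move from e to k and shrink the gap.

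**Example within that mortality range (assumed counts).** n = 15, 4 intubated, 3 of them die (75%), 1 extubated before Day 28, no other deaths. Exact (Clopper-Pearson) 95% intervals:

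| Row | Result | Exact 95% CI |
|---|---|---|
| Alive at Day 28 | 12/15 = 80.0% | 51.9–95.7% |
| Snapshot as written | 12/15 = 80.0% | 51.9–95.7% |
| Alive, never intubated | 11/15 = 73.3% | 44.9–92.2% |

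If that one survivor were still ventilated on Day 28, the snapshot would be 11/15 and the gap to the never-intubated rate would vanish.

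**Can the data support the cumulative rule?** Section 6.2 schedules pulmonary indices daily during study drug, then on Days 8, 15 and 28 for patients still in hospital. After baseline, the WHO scale is taken on Days 3, 8, 15 and 28. An intubation that starts and ends between Day 15 and Day 28 would appear in neither. Ventilation start and stop dates are therefore needed. The count of ventilated patients and the ventilator free-days cannot be completed without the same information.

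**The case against.** The strongest reply is that status at a fixed day is a legitimate endpoint, stated in full and without self-contradiction. It also carries information that the alternative discards, since the never-intubated rule scores a patient who has been extubated and has recovered the same as one who died. That stands, and it is the reason to keep the snapshot under a name that describes it.

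It is also true that earlier ventilation is not lost to the trial. The ventilated-patient count records it, and ventilator free-days would separate a patient ventilated from Day 3 to Day 27 from one never intubated. But the count is not combined with death, the free-days have no scoring rule, and Section 12.3 gives neither a specific analysis. The defined progression endpoint does not fill the gap, because its definition covers only patients with baseline PaO₂/FiO₂ of at least 200 and lists neither intubation nor death.

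Two stronger readings are tempting. A reader might infer that this endpoint merely repeats overall survival. The two differ by k/n, and they coincide only if nobody alive is ventilated on Day 28, which the documents give no ground to assume. A reader might also picture half of 4 intubated patients surviving and being extubated, for a gap of 2/15 = 13.3 points. That implies 50% ventilated mortality, below the range in Section 1.1.

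On non-invasive support, the plan already lists BiPAP and CPAP apart from mechanical ventilation. Only the bare word in Section 12.3 needs tying down.

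**Conclusion.** The point holds as a mismatch between a label and its scoring rule. What Section 12.3 calls ventilator-free survival can only equal or exceed the never-intubated survival rate that its name suggests, provided that *ventilator* means invasive ventilation. The excess is 6.7 points per extubated survivor at n = 15 and 8.3 at n = 12. The number of such patients is unknown. The expected gap of at most about 2 to 9 points at n = 15 rests on an assumed 4 intubations and on applying the cited mortality by Day 28.

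A reader might go further and conclude that the trial would report failures of treatment as successes. The documents do not support that. It is true of one row, while other listed endpoints record the intubation. This is a descriptive secondary endpoint in a pilot not sized on power, with safety as its primary endpoint. No test, sample size or stopping rule depends on it.

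**What to change.** In Section 12.3:

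1. Define Day 28 ventilator-free survival as alive at Day 28 with no invasive mechanical ventilation at any time from treatment start through Day 28, reported with an exact 95% confidence interval.
2. Keep the existing rule as a separate row named *alive and off ventilator at Day 28*, with the same type of interval.
3. State that *ventilator* means invasive mechanical ventilation (WHO score 6 or 7) and does not include BiPAP or CPAP.
4. Derive the first row from ventilation start and stop dates through Day 28, not from the scheduled WHO scores.
5. Reconcile the denominator of twelve with the 15 patients to be enrolled.

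The cost is a few sentences, plus ventilation dates that two listed endpoints already need. The drawback is a headline proportion that may be less favourable and that scores extubated survivors as failures. The snapshot row is kept to show those patients.
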